5.7.3 Precautions and Restrictions

Patients should not drive, operate dangerous tools or machinery, or engage in any other potentially hazardous activity that requires full alertness and coordination if they experience sedation while enrolled in this study.

Patients are to be instructed to limit the use of alcohol while enrolled in this study.

- Fluid deficit should be corrected before initiation of treatment and during treatment.
- Nonsteroidal anti-inflammatory drugs (NSAIDS) should be avoided with impaired renal function given reported NSAID-induced renal failure in patients with decreased renal function

5.8 Reproductive Considerations

It is not known what effects TAK-659 has on human pregnancy or development of the embryo or fetus. Therefore, female patients participating in this study should avoid becoming pregnant, and male patients should avoid impregnating a female partner. Nonsterilized female patients of reproductive age group and male patients should use effective methods of contraception through defined periods during and after study treatment as specified below.

Female patients must meet 1 of the following:

- Postmenopausal for at least 1 year before the screening visit, or
- Surgically sterile, or
- If they are of childbearing potential, agree to practice 1 highly effective methods of contraception and 1 additional effective (barrier) method, at the same time, from the time of signing of the informed consent form through 180 days(or longer, as mandated by local labeling [eg, USPI, SmPC, etc;]) after the last dose of study drug, or
- Agree to practice true abstinence, when this is in line with the preferred and usual lifestyle of the patient. (Periodic abstinence [eg, calendar, ovulation, symptothermal, postovulation methods], withdrawal, spermicides only, and lactational amenorrhea are not acceptable methods of contraception. Female and male condoms should not be used together.)
- Agree to not donate eggs (ova) during the course of this study or 180 days after receiving their last dose of study drug(s).

Male patients, even if surgically sterilized (i.e., status post-vasectomy) must agree to 1 of the following:

- Agree to practice highly effective barrier contraception during the entire study treatment period and through 180 days after the last dose of study drug, OR
- Agree to practice true abstinence, when this is in line with the preferred and usual lifestyle of the patient. (Periodic abstinence [eg, calendar, ovulation, symptothermal, postovulation methods for the female partner], withdrawal, spermicides only, and lactational amenorrhea are not acceptable methods of contraception. Female and male condoms should not be used together.)
- Agree not to donate sperm during the course of this study or 180 days after receiving their last dose of study drug.

Acceptable non-hormonal birth control methods:

- Total sexual abstinence ie, refrain from any form of sexual intercourse in line with the patients' usual and/or preferred lifestyle. Abstinence must be for the total duration of the study treatment and for at least 1 month (for female patients) or 3 months (for male patients) after the last dose of study treatment.
- NOTE: Periodic abstinence (eg, calendar ovulation, symptothermal, post-ovulation methods) and withdrawal are not acceptable methods of contraception.
- Vasectomised sexual partner PLUS male condom. With participant assurance that partner received post-vasectomy confirmation of azoospermia.
- Tubal occlusion PLUS male condom
- Intrauterine Device PLUS male condom. Provided coils are copper-banded.

Acceptable hormonal methods:

- Etonogestrel implants (eg, Implanon®, Norplant®) PLUS male condom
- Normal and low dose combined oral pills PLUS male condom
- Hormonal shot or injection (eg, Depo-Provera) PLUS male condom
- Intrauterine system device (eg, levonorgestrel-releasing intrauterine system –(Mirena®) PLUS male condom

6. TOXICITIES AND DOSE DELAYS/DOSE MODIFICATIONS

The NCI Common Terminology Criteria for Adverse Events (CTCAE) v5 will be used to grade adverse events.

Subjects enrolled in this study will be evaluated clinically and with standard laboratory tests before and at regular intervals during their participation in this study as specified in Study Calendar & Evaluations.

Subjects will be evaluated for adverse events (all grades), serious adverse events, and adverse events requiring study drug interruption or discontinuation as specified in Study Calendar & Evaluations.

6.1 Dose Delays/Dose Modifications

All toxicities that occur during the study will be actively managed following the standard of care unless otherwise specified in the protocol.

Patients who have the TAK-659 dose held due to treatment-related or possibly related AEs may resume study drug after resolution of the AE but may either maintain the same dose level or have doses of TAK-659 reduced (dose reduction) by at least 1 dose level. When a dose reduction occurs, the TAK-659 dose will be reduced to the next lower dose that either been established as a safe dose during dose escalation or is lower by a 20-mg increment. If initial dose adjustment does not provide sufficient relief, the dose of TAK- 659 can be further reduced if the treating physician considers that the patient is benefiting from study treatment and may benefit at a further reduced dose of TAK-659. When a dose reduction of TAK-659 is required due to toxicity, no dose re-escalation will be permitted.

If TAK-659 dosing is delayed for > 21 days for TAK-659-related or possibly related toxicities despite supportive treatment per standard clinical practice or more than 2 dose reductions are required in a patient, this patient should be considered to have study treatment discontinued, unless the treating physician considers that the patient may benefit from continued study treatment after resolution of AEs

to \leq Grade 1, or baseline, or a level considered acceptable by the physician. The patient will continue to be followed for 30 days for safety evaluation after the last administration of TAK-659.

Patients who experience a DLT (during escalation) or DLT-like toxicity (during phase 2 of the study) during the first cycle will, in general, require that treatment with TAK-659 be permanently discontinued. If, in the opinion of the investigator it is in the patient's best interest to continue treatment with TAK-659, then the dose of TAK-659 will be reduced by at least 1 dose level when treatment resumes after recovery of the toxicity or toxicities in question to \leq Grade 1 or to baseline values or to a level considered acceptable by the investigator. However, if a patient requires a dose delay of > 21 days for such an event to resolve despite the best supportive care permissible per protocol, then the patient must be discontinued from the study.

Detailed dose modification guidelines are provided in Section 6.2. In the case of TAK-659, which is administered once daily orally, a 1-step reduction of dose (by 20mg) may occur and if toxicity occurs at that dose, a second reduction may be considered. This second reduction will be subject to the judgment of the treating physician. In the case of Ixazomib, further reductions below the -2 dose step reduction from the starting dose that already exists below the RP2D in myeloma is not anticipated.

When a dose reduction occurs, no dose-reescalation will be permitted intrapatient. If study drug dosing is delayed for > 21 days despite supportive treatment per standard clinical practice or more than 2 dose reductions are required in a patient, this patient will have study treatment discontinued.

There exist both unique and overlapping toxicities of TAK-659 and Ixazomib, which will influence dose modification of one or both within the combination. As compared with its predecessor Bortezomib, Ixazomib possesses lower incidence of neuropathy, but the incidence of diarrhea may be higher. However, that diarrhea is usually below grade 3, except in 15-20 % cases in the phase I weekly administration trial. Both Ixazomib and Bortezomib affect thrombocytopenia, but in the context of AML induction therapy, thrombocytopenia is an intrinsic feature, which is supported by transfusion.

By contrast, diarrhea occurs as AE with TAK-659, at 32% rate, and the grade is not high, but in preclinical animal models, gastrointestinal hemorrhage and/or bowel intimal damage was noted at high doses. In the phase Ib C34002 AML trial, the major DLTs included hemorrhage, possibly related to thrombocytopenia, or to functional inactivation of the platelets, at the highest dose of TAK-659: 80 mg po bid. In addition, asymptomatic elevation of lipase, AST and ALT have been observed frequently, but pancreatitis or hepatitis are rare. Pneumonitis felt related to TAK-659 is rare.

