5.4 Definition of Dose Limiting Toxicity

Toxicity will be evaluated according to the NCI CTCAE version 5.

DLT is defined as any of the following events occurring within the first 2 cycles that are considered by the treating physician to be at least possibly related to therapy with study drug(s). AEs in which the relationship to study drug cannot be ruled out should be considered possibly related to study drugs TAK-659 and/or Ixazomib.

- Prolonged myelosuppression with the persistence of \geq Grade 4 neutropenia or thrombocytopenia in the absence of leukemia (blast count <5% in bone marrow) at least 42 days after the initiation of therapy.
- Any Grade 3 or greater nonhematologic toxicity with the following exceptions:
 - Grade 3 nausea and/or emesis resolved to \leq Grade 1 or baseline in a week after the use of an optimal antiemetic regimen based on standard practice. The optimal antiemetic regimen is defined as an antiemetic regimen that employs both a 5-hydroxytryptamine 3 serotonin (5-HT3) antagonist and a corticosteroid given in standard doses and according to standard schedules. Grade 3 nausea, vomiting must not require tube feeding, total parenteral nutrition, or require prolonged hospitalization.
 - Grade 3 diarrhea that resolved to \leq Grade 1 or baseline in a week after receiving the maximal supportive therapy based on standard practice. Grade 3 diarrhea must not require tube feeding, total parenteral nutrition, or require prolonged hospitalization.
 - Brief (<1 week) Grade 3 fatigue.
 - Electrolyte abnormalities correctable within 72 hours

- Grade 3 or 4 tumor lysis syndrome if it is successfully managed clinically and resolves within 7 days without end-organ damage.
- Failure to administer $\geq 75\%$ of planned doses of the study drug due to TAK-659- or Ixazomib-related or possibly related hematologic (considered not related to leukemic infiltration) or nonhematologic toxicities.
- Other TAK-659- or Ixazomib-related Grade 2 or greater nonhematologic toxicities that, in the opinion of the investigator, require a dose reduction or discontinuation of therapy.
- Confirmed Hy's law/guideline cases of drug-induced liver injury: ALT or AST $>3\times$ upper limit of normal and total bilirubin $>2\times$ ULN, which is not cholestatic (ALT value \div ALT ULN) \div [Alkaline phosphatase value \div Alk phos ULN] $= <2$), and not caused by disease. This will require permanent drug discontinuation.

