6.1.2 TAK-659 dose modifications for Nonhematologic Toxicities

Please refer to the Table below for dose held and dose reduction recommendations for non-hematologic toxicities. When the dose of TAK-659 is withheld based on the following criteria, clinical and laboratory re-evaluation should be repeated at least weekly or more frequently until the toxicity resolves to \leq Grade 1, or baseline, or a level considered acceptable by the treating investigator (must be \leq Grade 2). Upon recovery, TAK-659 may be reinitiated either at the same dose level or at a reduced dose level. For events in which there are transient lab value abnormalities that, based on investigator assessment, are not clinically significant or related to disease and not the drug, continuation of therapy without following the dose modification guideline is permissible after discussion with the sponsor investigator.

Criteria	Action
All Grade 3 Nonhematologic Toxicities with the exception of:	
 • Hold TAK-659 until resolution to Grade \leq 1 or baseline or a level considered acceptable by the investigator (must be \leq Grade 2). 
 ◦ If resolved in \leq 7 days, then maintain the dose level. ◦ If resolved in $>$ 7 days, then dose reduce by 1 dose level. ◦ If recurs, then dose reduce by 1 dose level. • For the exceptions listed, maintain dose level (no dose hold required). • Permanent discontinuation should be considered if the toxicities persist as \geq Grade 3 for more than 21 days despite temporary disruption of study drug.
Grade 4 Nonhematologic Toxicities	
 • Permanently discontinue TAK-659 for any grade 4 nonhematologic toxicities that are at least possibly related to TAK-659.

In general, the study drug(s) will resume only after the resolution of AEs to \leq Grade 1 or baseline or as specified in these dose modification guidelines. However, retreatment with study drug(s) could start when the AEs are resolved to a level deemed acceptable by the investigator. When a dose reduction of TAK-659 is required, no re-escalation of dose will be permitted.

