- Additional ECGs may be performed at more frequent intervals until repeated QTc measurements fall or are below the threshold interval that triggered the repeat measurement.

The decision whether to reinitiate TAK-659 treatment with or without dose reduction and additional monitoring in those patients who had asymptomatic prolonged QTc > 500 msec (Grade 3) that has reverted to an acceptable interval, have previously tolerated TAK-659, and appear to have benefitted from TAK-659 treatment with either disease control or response will be agreed to by the local investigator and the sponsor investigator on a case-by-case basis.

The ECGs performed should be reviewed by the local investigator or his/her delegate before the patient leaves the clinic on visit days.

Hematology

Will include: Hemoglobin; Leukocytes with differential; Hematocrit; Neutrophils (absolute neutrophil count [ANC]); Platelet (count); Percentage of leukemic blast cells

Serum Chemistry

Will include: Blood urea nitrogen (BUN); Albumin; Calcium; Alkaline phosphatase; Chloride; Creatinine; Carbon dioxide (CO₂); Bilirubin (total) Aspartate aminotransferase (AST); Alanine aminotransferase (ALT); Uric acid; Magnesium; Lactate dehydrogenase (LDH); Amylase; Lipase; Total protein; Gamma glutamyl transferase (GGT); Glucose; Phosphate; Sodium; Potassium

Urinalysis

Turbidity and Color; Ketones; Urobilinogen; pH; Bilirubin; Glucose; Specific gravity; Occult Blood; Leukocytes; Protein; Nitrite

Ophthalmic Exam

A slit lamp eye examination will be performed by an ophthalmologist at Screening; on Cycle 2 Day 1; on Cycle 7 Day 1; every 6 cycles thereafter (+/- 2 weeks); and at the Safety follow up. On the basis of nonclinical toxicology findings with TAK-659 in rats, slit lamp examinations should focus on detecting any posttreatment changes in ocular lens. Examination and photographing of the retina will be performed at baseline but not during the study unless clinically indicated. Additional eye exams may also be performed, as required. Additionally, patients will be carefully monitored for eye complaints at each visit and instructed to report visual symptoms as soon as they occur.

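### A first-cycle Grade 3 DLT that resolves within 7 days must be stopped or dose-reduced under Section 6.1 but keeps its TAK-659 dose under the Section 6.1.2 table, and no rule says which governs

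*Combined protocol and SAP*

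**What the plan says.** **DLT definition (Section 5.4).** Among events in the first two cycles judged at least possibly related to study drug, the list of DLTs includes "Any Grade 3 or greater nonhematologic toxicity with the following exceptions". The exemptions are nausea or emesis and diarrhea that settle within a week, brief fatigue, electrolyte changes corrected within 72 hours, and tumor lysis syndrome that is managed and resolves. There is no general exemption for events that resolve within 7 days.

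**First-cycle rule (Section 6.1).** A DLT in escalation, or a DLT-like toxicity in Phase II, "during the first cycle will, in general, require that treatment with TAK-659 be permanently discontinued". If the investigator judges that continuing is in the patient's interest, "then the dose of TAK-659 will be reduced by at least 1 dose level when treatment resumes after recovery".

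**Non-hematologic rule (Section 6.1.2).** The introductory text states: "Upon recovery, TAK-659 may be reinitiated either at the same dose level or at a reduced dose level". The table then addresses Grade 3 non-hematologic toxicities. TAK-659 is held, and for an event that resolves within a week the instruction reads "7 days, then maintain the dose level". Events that last longer than 7 days, or recur, lead to a one-level reduction. Excepted events keep their dose level without a hold.

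**Cross-reference.** Section 6.1 says "Detailed dose modification guidelines are provided in Section 6.2". Section 6.2 contains only the ladder of dose levels and the stopping rule for delays over 21 days or more than two reductions.

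**The concern.** A site facing a related, non-exempt Grade 3 event in Cycle 1 that clears within a week can follow either section and be compliant with it. If it follows the table, the patient returns to full-dose TAK-659 after a DLT. If it follows 6.1, the patient stops, or restarts lower with no later re-escalation.

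The first consequence is for patient safety and for consistent handling across the 2 to 4 planned centers (Section 5.1). The second is for dose selection. Section 5.3 requires that more than 80% of the expected dose be administered within a cohort as the tolerability criterion for the RP2D, and the two rules produce different delivered doses from the same clinical event.

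**Working it through.** **Step 1. The same event under each rule.** Take a Grade 3 rash judged possibly related to TAK-659, starting on Cycle 1 Day 8 at 100 mg daily, with doses on Days 8 to 12 held and the event then resolved.

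| Rule | Result |
|---|---|
| 5.4 | Related, Grade 3, non-hematologic, not exempt: a DLT |
| 6.1 | Stop TAK-659, or resume at 80 mg or lower |
| 6.1.2 table | Resolved within 7 days: resume at 100 mg |
| 6.2 | Gives the dose ladder (100, 80, 60 mg) but no precedence |

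The phrase in 6.1 that softens the rule applies only to stopping. The fallback reduction is worded as mandatory. No option under 6.1 returns this patient to 100 mg.

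**Step 2. Does the table's exception list matter?** The list is not legible in the available text, which is not a fault of the plan. It cannot remove the conflict, because an excepted event also keeps its dose level.

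**Step 3. Which events do not conflict.** Events lasting more than 7 days or recurring are reduced under the table too. Events exempt under 5.4 are not DLTs by that criterion. Transient laboratory abnormalities may fall under the waiver in 6.1.2, or may not count as adverse events under 12.1.1.

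**Step 4. Delivered dose for one affected patient.** Section 5.3 does not define expected dose or its time window. I assume TAK-659 alone, over the two-cycle DLT window, with no later event:

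Expected = 2 cycles × 15 doses × 100 mg = 3000 mg. Seven doses (700 mg) precede onset, five are held, three remain in Cycle 1, and 15 follow in Cycle 2.

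- Table: 700 + 3 × 100 + 15 × 100 = 2500 mg; 2500/3000 = 83.3%
- 6.1, reduced to 80 mg: 700 + 3 × 80 + 15 × 80 = 2140 mg; 2140/3000 = 71.3%
- 6.1, stopped: 700 mg; 700/3000 = 23.3%

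Varying onset from Day 4 to Day 11 and the hold from 3 to 7 days gives 76.7–90.0%, 63.3–78.7% and 10.0–33.3% respectively.

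**Step 5. Effect on a cohort of six.** One DLT in six is 1/6 = 16.7%, inside the safety criterion of under 20% in Section 5.3. For the cohort mean to exceed 80%, the other five must average above (6 × 0.80 − patient's share)/5:

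- Table: (4.80 − 0.833)/5 = 79.3%
- Reduced: (4.80 − 0.713)/5 = 81.7%
- Stopped: (4.80 − 0.233)/5 = 91.3%

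**Step 6. If the example event were on the exception list.** There would be no hold under the table, so delivered dose would be 3000/3000 = 100% and the other five would need (4.80 − 1.00)/5 = 76.0%. The gap from the 6.1 outcomes would widen.

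**The case against.** The best counter-argument is that the text can be harmonised. Section 6.1 itself gives a general rule for held doses (same level or lower) and then a specific rule for first-cycle DLTs. The 6.1.2 text largely repeats the general rule, calls its table recommendations, and sits beneath 6.1. On that reading the DLT paragraph governs and only a cross-reference is missing. The reading is tenable, and probably what was intended, but it appears nowhere in the plan. Specificity also cuts the other way: 6.1.2 is narrower by toxicity type, grade and time to resolution, and it is the table a site would open for this event.

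The objection on frequency largely stands. The common Grade 3 or higher related non-hematologic events for TAK-659 in Section 1.4.6 are laboratory findings, many of them asymptomatic, and some would fall under the waiver or an exemption. The rates given there are pooled over cycles and not split by time to resolution, so they give no count. Rash, used above for clarity, is documented mainly for ixazomib.

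The effect on the tolerability criterion is also modest unless the drug is stopped: table against one-level reduction moves the mean required of the other patients from 79.3% to 81.7%. Weekly Phase I safety calls (Section 14.1) and central review of toxicity before dose decisions (Section 14.3) would limit divergence between sites. They do not tell a site what dose to restart on the day.

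Section 8.1 also permits restart after Grade 3 QTc prolongation with or without reduction. That is a case-by-case agreement with its own conditions, and this point does not rest on it.

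**Conclusion.** The concern holds. For a related, non-exempt Grade 3 non-hematologic event in Cycle 1 that resolves within 7 days, Sections 6.1 and 6.1.2 give incompatible TAK-659 instructions and nothing in the plan ranks them. Applied as written, the table returns a patient to full dose after a DLT. The conflict is clearest in Phase I, since the DLT-like toxicity of Phase II is not separately defined.

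Per affected patient, the choice of rule moves delivered dose from 83.3% to 71.3% or 23.3%, given the assumed 3000 mg two-cycle base, Day 8 onset and five-dose hold. How many patients this would touch cannot be derived from the documents and is likely small. The event counts as a DLT whichever section is followed, so DLT counts, 3+3 decisions and the Phase II error rates do not change. The point should be fixed because it is a safety instruction.

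**What to change.** Add to Section 6.1.2 that a first-cycle DLT, or DLT-like toxicity in Phase II, is handled under Section 6.1: stop TAK-659, or resume at least one dose level lower after recovery. Restrict the table's line for events resolved within 7 days, and its line for excepted events, to events that are not first-cycle DLTs. Apply the same limit to the introductory sentence allowing restart at the same dose.

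The cost is wording only. No patients, visits or analyses are added.

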6.1.1 TAK-659/Ixazomib Dose Adjustments for Hematologic Toxicities

Blood counts should be regularly monitored during the study as specified in the Schedule of Events and tested more frequently if clinically indicated based on local standard practice. Comparison to baseline values and AE grading based on CTCAE (v.5) will be performed. When severe hematological AE's occur (\geq Grade 4 events, febrile neutropenic infection, thrombocytopenia with signs of overt bleeding or clinically significant bleeding), close monitoring and medical management using supportive care if indicated will be given based on standard practice (See Section 6.3) while the study drug should be continued. If these events persist despite supportive care (not resolved to \leq Grade 1, or baseline, or a level considered acceptable by the investigator within 7 days), at the investigator's discretion, bone marrow aspirate assessment will be performed to evaluate whether the prolonged myelosuppression is due to leukemic infiltration or disease progression. If leukemic blasts are $\leq 5\%$ in bone marrow and

bone marrow aplasia is seen, the study drugs should be continued for completion of the current cycle if less than 14 days, with repeat bone marrow aspirate in the absence of peripheral hematologic recovery to assess marrow cellularity. In the absence of evidence for bone marrow recovery, the study drugs should be withheld for up to 21 days. Clinical and laboratory re-evaluation should be repeated at least weekly or more frequently until recovery to \leq Grade 1 or baseline or a level considered acceptable by the investigator. Upon recovery, TAK-659 may be reinitiated (along with Ixazomib) at the same dose level or at a reduced dose level at the discretion of the investigator. If no recovery occurs within 21 days (based on peripheral blood counts and/or repeat bone marrow aspirate) after the study drug hold (42 days in total after the first dose on Cycle 1, Day 1), the patient should discontinue study treatment, and if this occurs in Cycle 1, the patient will be considered to have a DLT. The patient will continue to be followed until resolution or stabilization of the event, initiation of another anti-leukemia therapy, or overt AML progression, whichever occurs first.

When a dose reduction of TAK-659 or ixazomib is required in a patient, no re-escalation of dose will be permitted.

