6.1.3 Ixazomib Dose Adjustments for Hematologic Toxicities

Ixazomib Dose Adjustments for Hematologic Toxicities	
Criteria	Action
Within-Cycle Dose Modifications In Induction (< 2 cycles and marrow blasts present)	
 Dose reduction is not required
Within-Cycle Dose Modifications In consolidation (after documentation of morphologic blast clearance, generally beginning after the second cycle)	
 See below

 If platelet count $\leq 20 \times 10^9/L$ or ANC $\leq 0.20 \times 10^9/L$ on a ixazomib dosing day (other than Day 1) 	
 Ixazomib dose should be withheld. Complete blood count (CBC) with differential should be repeated at least twice weekly until the ANC and/or platelet counts have exceeded the prespecified values. Upon recovery, ixazomib may be reinitiated with 1 dose level reduction.
Dose Modifications for Subsequent Treatment Cycles	
 Delay of 1 week in the start of a subsequent cycle due to lack of toxicity recovery as ANC $< 0.5 \times 10^9/L$, platelet count $< 30 \times 10^9/L$ Hold ixazomib until resolution as per criteria Upon recovery, reduce ixazomib 1 dose level. The maximum delay before treatment should be discontinued will be 2 weeks or at the discretion of the PI.
Dose Modifications for Subsequent Treatment Cycles	
 All hematologic toxicities For hematologic toxicity that occurs during a cycle but recovers in time for the start of the next cycle,: 
 If dose was reduced within the cycle, start the next cycle at that same dose. If due to toxicity timing, ie, after Day 15 dosing thus a dose reduction was not required at that point in the cycle, reduce ixazomib by 1 dose level at the start of that cycle. Do not reduce the dose both within a cycle and at the start of the cycle for the same most severe toxicity.

Ixazomib Treatment Modification (Delays, Reductions, and Discontinuations) Due to Adverse Events (Non-Hematologic Toxicities)		
Adverse Event (Severity)	Action on Study Drug	Further Considerations
Peripheral Neuropathy: Grade 1 peripheral neuropathy	
 • No action 	Grade 1 signs and symptoms: asymptomatic; without pain or loss of function; clinical or diagnostic observations only [27]

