New or worsening Grade 1 peripheral neuropathy with pain or Grade 2	
 • Hold study drug until resolution to Grade ≤ 1 or baseline 	Grade 2 signs and symptoms: Moderate symptoms; limiting instrumental activities of daily living (ADL) [27]
New or worsening Grade 2 peripheral neuropathy with pain or Grade 3	
 • Hold study drug until resolution to Grade ≤ 1 or baseline • Reduce study drug to next lower dose upon recovery 	Grade 3 signs and symptoms: severe symptoms; limiting self-care ADL; assistive device indicated [27]
New or worsening Grade 4 peripheral neuropathy	
 • Discontinue study drug 	
Grade 2 Rash	
 • Symptomatic recommendations as per section 6.3 	The investigator and project clinician may discuss considerations for dose modifications and symptom management.
Grade 3 nonhematologic toxicity judged to be related to study drug	
 • Hold study drug until resolution to Grade < 1 or baseline 	Symptomatic recommendations noted in Section 6.3
If not recovered to $<$ Grade 1 or baseline within 4 weeks	
 • Reduce study drug 1 to next lower dose upon return to $<$ Grade 1 or baseline 	
Subsequent recurrence Grade 3 that does not recover to $<$ Grade 1 or baseline within 4 weeks	
 • Hold study drug until resolution to Grade < 1 or baseline • Reduce study drug to next lower dose 	Monitor closely, take appropriate medical precautions, and provide appropriate symptomatic care
Grade 4 nonhematologic toxicities judged to be related to study drug	
 • Consider permanently discontinuing study drug 	Exceptions are cases in which the investigator determines the patient is obtaining a clinical benefit

Once ixazomib is reduced for any toxicity, the dose may not be re-escalated.

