6.4 Protocol Therapy Discontinuation

Patients will be informed that they have the right to withdraw from the study at any time for any reason, without prejudice to their medical care. In addition to discontinuation from therapy related to toxicities as outlined in section 6.1, a subject will also be discontinued from protocol therapy and followed up per protocol under the circumstances outlined below. The reason for discontinuation of protocol therapy will be documented on the electronic case report form (eCRF).

- Documented disease progression
- The treating physician determines a change of therapy would be in the best interest of the subject
- The subject requests to discontinue protocol therapy, whether due to unacceptable toxicity or for other reasons
 - If a subject decides to prematurely discontinue protocol therapy (“refuses treatment”), the subject should be asked if he or she may still be contacted for further scheduled study assessments. The outcome of that discussion should be documented in both the medical records and in the eCRF.
- A female subject becomes pregnant
- If protocol therapy is interrupted for ≥ 21 days.
- Protocol violation or non-compliance of the patient
- Study terminated
- If the responsible physician thinks a change of therapy would be best for the patient
- Noncompliance of the patient
- Pregnancy
- Death

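### The rules on how long treatment may be held before it must stop contradict each other: beyond 21 days, the same hold can end therapy under one section and continue it under another.

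*Combined protocol and SAP*

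**What the plan says.** The limits on holding treatment are spread over six places in Section 6.

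- **Section 6.1, TAK-659 paragraph.** "If TAK-659 dosing is delayed for > 21 days for TAK-659-related or possibly related toxicities", or if more than two dose reductions are needed, treatment is regarded as discontinued, "unless the treating physician considers that the patient may benefit from continued study treatment after resolution of AEs" to an acceptable grade.
- **Section 6.1, first-cycle DLT or DLT-like toxicity.** "if a patient requires a dose delay of > 21 days for such an event to resolve", the patient must come off the study. No override is given.
- **Section 6.1, later paragraph covering both drugs.** "If study drug dosing is delayed for > 21 days despite supportive treatment", treatment will be stopped. No override is given. The footnote to the Section 6.2 table repeats the rule.
- **Section 6.1.1, haematologic, both drugs.** The drugs may be withheld for up to 21 days. "If no recovery occurs within 21 days (based on peripheral blood counts and/or repeat bone marrow aspirate) after the study drug hold", the patient should stop.
- **Section 6.1.2, TAK-659 Grade 3 non-haematologic.** If the toxicity stays at Grade 3 or above for more than 21 days, stopping is something to consider.
- **Section 6.1.3, ixazomib cytopenia delaying a cycle.** "The maximum delay before treatment should be discontinued will be 2 weeks or at the discretion of the PI".
- **Section 6.1.3, ixazomib non-haematologic table.** Related Grade 3 toxicity is held until recovery. If it has not recovered to below "Grade 1 or baseline within 4 weeks", the dose is lowered one step on recovery and treatment goes on.
- **Section 6.4.** One listed reason for ending therapy is "If protocol therapy is interrupted for" 21 days or more.

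**The concern.** A maximum-delay rule should give one answer for a given drug, toxicity and length of hold. Here some rules compel discontinuation, some leave it to the physician, and one plans resumption after the compulsory limit has passed. The study is multicentre (Section 5.1 expects about 2 to 4 centres), so two sites could treat identical patients differently and both be compliant.

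Patient safety is at stake first. The off-treatment date is next, and other timings depend on it: Section 8.6 times the safety visit from the last dose, and Section 8.7 runs survival follow-up for up to 12 months after the study drug is discontinued. In phase II, the rule a site applies could also decide whether a patient stays on long enough for the Cycle 3 marrow that Section 8.3 uses to grade best response.

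**Working it through.** No sample size or error rate is involved, so the check is to fix a length of hold and read off what each rule requires.

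| Hold | Rules that end treatment | Rules that let it continue |
|---|---|---|
| 15–20 days, ixazomib cytopenia delaying a cycle | 6.1.3 cytopenia row, unless the PI decides otherwise | 6.1, 6.1.1, 6.2, 6.4 (limit not reached) |
| Exactly 21 days | 6.4 | 6.1 and 6.2 (both need more than 21) |
| 22 days or more, TAK-659-related | 6.1 later paragraph, 6.2; also 6.4 on its face | 6.1 TAK-659 paragraph (physician override); 6.1.2 for Grade 3 non-haematologic toxicity (stopping only considered) |
| More than 28 days, ixazomib-related Grade 3 non-haematologic | 6.1 later paragraph, 6.2; also 6.4 on its face | 6.1.3 non-haematologic table (reduce and resume on recovery) |

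**Row 3** is a direct contradiction within Section 6.1. Both paragraphs cover the same TAK-659 delay; one carries an override and the other does not. The exception is a first-cycle DLT or DLT-like toxicity, for which Section 6.1 has its own rule without an override, so the general override should not be read into that case.

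**Row 4** depends on whether *study drug* in Sections 6.1 and 6.2 includes ixazomib. The context suggests that it does. The Section 6.1 sentence comes soon after a paragraph on reductions of both drugs, and the Section 6.2 footnote sits under a table with a column for each. If ixazomib is included, the 4-week row cannot operate: it is reached after 28 days, and treatment ended once the delay passed 21, at least 28 − 21 = 7 days earlier.

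**Rows 1 and 2** are smaller. Row 2 differs on a single day. In row 1 the gap is 21 − 14 = 7 days, and PI discretion can close it.

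None of these rules says whether a hold of one drug that passes its limit ends both drugs or only that one.

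**The case against.** The strongest reply is that the rules differ because their scopes differ. Some are for TAK-659 and some for ixazomib; some are for cytopenia and some for other toxicity. Section 6.4 also introduces its list as additional to the toxicity rules of Section 6.1, so its 21-day entry need not compete with them. It may also mean interruption of the whole regimen, which an ixazomib-only hold would not be.

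Part of this stands. Section 6.4 is a weak source of conflict and is treated here as a minor mismatch. But scope does not resolve the two main contradictions. The Section 6.1 paragraphs overlap on the same TAK-659 delay, and the general *study drug* rule is not limited by drug or toxicity. Nothing says that the specific rule prevails over the general one.

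Four stronger readings are tempting but unsupported.

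- *Every hold of 15 days or longer is in conflict.* Only the ixazomib cytopenia row has a limit that short, and it allows PI discretion. A non-haematologic hold of 15 to 20 days meets no discontinuation limit.
- *Four weeks is a competing maximum.* That table states no maximum; it says what to do when recovery takes longer.
- *The delay limit changes DLT counts through the 75%-of-doses criterion.* A related Grade 3 non-haematologic toxicity lasting about 30 days in phase I Cycles 1–2 would generally already be a DLT under Section 5.4, whichever delay rule is used.
- *The Simon decision is distorted.* Section 8.5 counts response-evaluable patients who stop before three cycles, and Section 13.2 uses best response by the end of Cycle 3, so an earlier response still counts. The patient at risk is one whose first response would come after a disputed hold.

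**Conclusion.** The point holds as an inconsistency in the text. Two contradictions are substantive: the TAK-659 delay beyond 21 days (Sections 6.1 and 6.1.2 against Sections 6.1 and 6.2), and ixazomib resumption after more than 4 weeks (Section 6.1.3 against Sections 6.1 and 6.2). The second assumes that *study drug* includes ixazomib. The mismatches in Section 6.4 and in the ixazomib cytopenia row are minor.

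Opposite but compliant stopping decisions are possible mainly for holds of 21 days or longer. The consequences for safety and off-treatment dates are direct. An effect on whether a patient reaches the Cycle 3 assessment is possible, but its size is unknown because the documents do not say how often such holds occur. The point does not show that dose escalation or the two-stage decision is compromised.

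**What to change.** Reconcile Sections 6.1, 6.1.1, 6.1.2, 6.1.3, 6.2 and 6.4 into one consistent maximum-delay rule per drug and toxicity type. For each rule, state:

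- the limit, with the same inequality sign everywhere;
- whether a hold of one drug beyond its limit ends both drugs or only that one;
- whether the limit may be overridden, and by whom;
- how it relates to the first-cycle DLT rule and to the list in Section 6.4.

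Sections 6.1.1 and 6.1.2 need to be included; otherwise the 21-day haematologic limit and the softer TAK-659 wording would still disagree with the rest. The limits themselves are for the sponsor to choose. The cost is protocol wording only, with no change to sample size, endpoints or analysis.
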